# 14.5 Visit 5: 9 weeks after starting YF476

The investigator will:

- check that the patient has fasted;
- collect the diary card, and issue a new one;
- check the diary card for compliance with treatment, and for adverse events and concomitant medication;
- collect YF476 container and assess compliance;
- record a 12-lead ECG, and blood pressure and heart rate;
- collect blood and urine for safety tests, including a pregnancy test for women of child-bearing potential;
- collect blood for assay of fasting levels of gastrin, CgA, YF476 (trough), and serum for storage;
- after collecting the fasting blood sample, give the patient their dose of YF476, wait 1 h, and then collect blood for assay of peakYF476 concentration;
- issue a fourth container of YF476 capsules (25 mg); 2 capsules to be taken once daily with breakfast **or**, if the dose was increased at Visit 4, 3 or 4 capsules once daily with breakfast; and
- remind the patient to fast before their gastroscopy on Visit 6.

#### 14.6 Visit 6: 12 weeks after starting YF476

The investigator will:

- check that the patient has fasted;
- collect the diary card;
- check the diary card for compliance with treatment, and for adverse events and concomitant medication;
- collect YF476 container and assess compliance;
- do a medical examination, including blood pressure and heart rate measurements, and 12-lead ECG;
- collect blood and urine for safety tests, including a pregnancy test for women of child-bearing potential;
- collect blood for assay of fasting levels of gastrin, CgA, YF476 (trough), and serum for storage;
- do a gastroscopy and take gastric biopsies, and proceed as follows:
  - if on visual inspection the gastric carcinoids have regressed completely, proceed to Visit 7; remind the patient to fast before their gastroscopy on Visit 7, or
  - if on visual inspection gastric carcinoids are still present, the patient leaves the trial.
- after collecting the fasting blood sample and doing the gastroscopy, give the patient their dose of YF476, wait 1 h, and then collect blood for assay of peak concentration of YF476.

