#### 6.2 Screening and treatment periods

	Visit 1: Visit 2:		Treatment period				Visit 7: 12 weeks after
	Screening	Screening 	Visit 3: 3 weeks	Visit 4: 6 weeks	Visit 5: 9 weeks	Visit 6: 12 weeks	stopping YF476
Informed consent	Х						
Medical history	X						
Inform GP	X						
Medical examination	Х			Х		X	
12-lead ECG	Х		Х	Х	Х	X	
Vital signs	Х		Х	Х	X	X	
Safety tests of blood & urine	Х		Х	Х	Х	Х	
Fasting serum gastrin, plasma CgA and serum for storage	Х		Х	Х	X	X	Х
Plasma YF476			$X^7$	X 	X 	X 	
Pregnancy test 	X	X	Х	X	X	X	
H. pylori test 	Х						
Gastroscopy 		X		X 		X 	X 
Collect & check diary card			Х	Х	Х	X	
Collect & check YF476 container for compliance			Х	Х	Х	X	
Issue YF476 capsules		Х	Х	X 	X 		
Issue diary card		Х	Х	X	X		
AE & concomitant medication enquiry			<	<>			

1. Women of child-bearing potential

2. Fasting from food and fluids for at least 6 hours before gastroscopy

3. Patients who meet the entry criteria, start 50 mg YF476 by mouth once daily at home on the day after Visit 2.

4. If gastroscopy at Visit 4 reveals complete regression of carcinoids on visual inspection, stop YF476, omit Visits 5 & 6, and proceed to Visit 7. If gastroscopy at Visit 4 reveals continuing presence of carcinoids on visual inspection, increase dose of YF476 to 75 or 100 mg *once* daily (optional).

5. If gastroscopy at Visit 6 reveals no regression of carcinoids, omit Visit 7.

6. *H. pylori* test will be done according to local SOPs, only if status is unknown.

7. Patients fast overnight before visit and bring their container of YF476 with them. They take YF476 only after collection of blood samples for trough YF476, fasting serum gastrin and CgA levels, and gastroscopy (if applicable). Patients stay 1 h after dosing for collection of blood sample for peak YF476 level

Visit 8 	Visit 9 	Visit 10 	Visit 11 	Visit 12 
Consent to extended dosing.	Safety &	Safety & efficacy	Safety &	Safety & efficacy
Some patients  might have a	efficacy check 	check  & gastroscopy 	efficacy check 	check  & gastroscopy 
new baseline gastroscopy and	after 12 weeks	after 24 weeks of	after 36 weeks	after 52 weeks of

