#### 9 Overall trial design

Patients will attend the clinic up to 12 times. The time that patients take to complete the trial will depend on their response to YF476.

At Visit 1, patients will be screened (excluding gastroscopy) for eligibility.

At **Visit 2**, patients will undergo gastroscopy and gastric biopsies. If they meet all the inclusion/exclusion criteria, they will start treatment with 50 mg YF476 by mouth *once* daily at home on the next day. Each subject will be given a unique number at the start of treatment.

They will complete a diary card daily throughout the treatment period.

**Visit 3** will be 3 weeks after starting YF476, to assess tolerability, safety and blood levels of gastrin, CgA and YF476.

**Visit 4** will be 6 weeks after starting YF476, to assess tolerability and safety, to repeat the gastroscopy and gastric biopsies, and to take blood samples to assess levels of gastrin, CgA and YF476. If the gastric carcinoids have regressed completely on visual inspection, YF476 will be stopped, Visits 5 and 6 will be omitted, and the patient will proceed to Visit 7. If the gastric carcinoids are still present, YF476 will be continued, but the dose may be increased to 75 or 100 mg *once* daily, at the discretion of the investigator.

**Visit 5** will be 9 weeks after starting YF476, to assess tolerability, safety and blood levels of gastrin, CgA and YF476.

**Visit 6** will be 12 weeks after starting YF476, to assess tolerability and safety, to repeat the gastroscopy and gastric biopsies, and to take blood samples to assess levels of gastrin, CgA and YF476. If the carcinoids have not regressed, the patient will leave the trial. If the carcinoids have regressed, the patients will proceed to Visit 7.

**Visit 7** will be a follow-up visit, 12 weeks after the end of treatment with YF476, only for patients who respond to YF476. The gastroscopy and blood sampling for fasting gastrin and CgA will be repeated.

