#### **Extended treatment**

Some patients will be eligible for extended treatment with YF476, as described below. To be eligible for further treatment, the patient must have benefitted from 12 weeks' treatment, and have tolerated YF476 well, and must give fully informed written consent.

**Visit 8** will be to inform the patient about the extended dosing period and prescribe YF476 capsules. If the investigator thinks that a new baseline gastroscopy and blood sampling (for safety, gastrin and CgA) is necessary, this will be carried out.

**Visit 9** will be 12 weeks after starting extended treatment with YF476, to assess tolerability, safety and blood levels of gastrin, CgA and YF476.

**Visit 10** will be 24 weeks after starting extended treatment with YF476, to assess tolerability and safety, to repeat the gastroscopy and gastric biopsies, and to take blood samples to assess blood levels of gastrin, CgA and YF476.

**Visit 11** will be 36 weeks after starting extended treatment with YF476, to assess tolerability, safety and blood levels of gastrin, CgA and YF476.

**Visit 12** will be 52 weeks after starting extended treatment with YF476, to assess tolerability and safety, to repeat the gastroscopy and gastric biopsies, and to take blood samples to assess levels of gastrin, CgA and YF476.

A formal follow-up visit will be omitted, as the patients are closely followed by the investigator as part of their standard healthcare.

The end of the trial will be the last visit by the last subject.

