### 14.7 Visit 7: 12 weeks after stopping YF476

Visit 7 will be a follow-up visit for patients who respond to YF476. The gastroscopy and blood sampling for fasting gastrin and CgA will be repeated.

Some patients will be eligible for extended treatment with YF476, as described below. To be eligible for further treatment, the patient must have benefitted from 12 weeks' treatment, and have tolerated YF476 well, and must give fully informed written consent.

### 14.8 Visit 8

The investigator will:

• tell the patient about the extended dosing period and ask him or her to read the information about the extended dosing and sign the consent form;

- do a gastroscopy and take gastric biopsies if the investigator thinks that a new baseline gastroscopy is necessary. If this is the case, the patient will have been told in advance and will be asked to fast for ≥6 h before the visit;
- collect blood for safety tests and for assay of fasting levels of gastrin and CgA if the investigator thinks that new baseline values are necessary;
- give the patient a container of YF476 capsules (25 mg) and instructions on how many to take daily with breakfast, starting the following day; and
- give the patient a diary card, to record YF476 doses, any adverse events, and any concomitant medication.

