# 14.10 Visit 10: 24 weeks after starting extended YF476 dosing

The investigator will repeat the procedures from visit 9 and:

- do a gastroscopy and take gastric biopsies, and proceed as follows:
  - if on visual inspection the gastric carcinoids have regressed completely: stop YF476, omit Visits 11 and 12, providing all safety assessments prove satisfactory; or
  - if on visual inspection gastric carcinoids are still present: continue treatment with YF476 once daily.

• after collecting the fasting blood sample and doing the gastroscopy, give the patient their dose of YF476, wait 1 h, and then collect blood for assay of peak YF476 concentration; and instruct the patient about Visit 11.

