### Efficacy data

The objective of this pilot study is to estimate the therapeutic response rate in the patients who receive YF476. The primary endpoint of the clinical response is defined as a 25% reduction in the size or number of endoscopically evident type I gastric carcinoids or a reduction of 25% in the gastric ECL cell density. Secondary endpoints include safety and changes in levels of biochemical markers (eg gastrin, CgA), histologic grade and quantitative PCR for ECL cell-specific products.

All variables will be summarised by descriptive statistics as appropriate. The mean or median of the following variables will be expressed as a percentage change of the mean or median response (as appropriate) compared to the baseline period: number of CgA ir-cells per unit area of mucosa CgAmuc and volume density of CgA ir-cells  $\rho_{CgA}$ ,

The data during the treatment period will be compared with baseline using ANOVA, with visit as fixed effect and subject as random effect. If insufficient data are available, the treatment comparison using ANOVA will not be done. Variables and parameters will be transformed before analysis, as appropriate.

Data from all subjects who complete the study without major protocol deviations will be included in the analysis of efficacy. The primary aim of the trial is to find out if YF476 can cause regression of gastric carcinoid tumours.

Interobserver variability will be reported to both endoscopic and histologic interpretations. A blinded endoscopist, who is unaware of the patient history, dose of YF476, or timing of the endoscopic examination, will review a random sample of endoscopic images to report the size of endoscopic lesions. In addition, a blinded pathologist, who is unaware of the patient history, dose of YF476, or timing of biopsy specimen, will review a random sample of histologic images to report the histologic grade and ECL cell density of the biopsy sample. Kappa statistics will be calculated to report the degree of agreement between the study and blinded endoscopists and between the study and blinded pathologists.

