# 18.2 Determination of sample size

The trial is an exploratory, open, pilot trial, so a power calculation is inappropriate. Gastric carcinoids are a rare condition, so the protocol sets a limit of up to 10 patients.

The results will be reviewed regularly, and if the results are unfavourable, the study will be stopped. If the results are favourable, the sponsor will set up a larger trial, probably double-blind, randomised, and placebo-controlled in design, and with a fixed dose of YF476.

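### Section 14.6 discharges partial regressors at Visit 6, while the summary, Section 9 and both flow charts send them on to Visit 7

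*Protocol*

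**What the plan says.** **Visit 6, detailed procedures (14.6).** Only complete regression on visual inspection leads to Visit 7. Otherwise, "if on visual inspection gastric carcinoids are still present, the patient leaves the trial".

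**Visit 6, elsewhere.** Section 9 says "If the carcinoids have regressed, the patients will proceed to Visit 7", and that a patient leaves if they have not regressed. The summary (2.6) says the same. Note 3 to flow chart 6.1 omits Visit 7 only when carcinoids have not regressed, and note 5 to 6.2 reads "If gastroscopy at Visit 6 reveals no regression of carcinoids, omit Visit 7".

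**Visit 7 (14.7).** "Visit 7 will be a follow-up visit for patients who respond to YF476". The word for responding is not tied to any definition there.

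**Response (18.1, Efficacy data).** The primary endpoint is "defined as a 25% reduction in the size or number of endoscopically evident type I gastric carcinoids", or a 25% reduction in gastric ECL-cell density.

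**Extension (2.6, 9 and 14.7).** To enter, "the patient must have benefitted from 12 weeks' treatment", must have tolerated YF476 and must consent again. Benefit is not defined. Under 14.4, a patient with complete regression at Visit 4 stops YF476 at week 6 and skips Visits 5 and 6.

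**The concern.** Partial regression is neither complete regression nor absence of regression, so the protocol gives such a patient two opposite instructions. The looser wording cannot simply be read as meaning complete regression. Section 9 specifies complete regression for Visit 4 and plain regression for Visit 6, and notes 4 and 5 to flow chart 6.2 make the same distinction.

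The stake is the off-treatment information. Visit 7 is the only mandated gastroscopy after YF476 has stopped: the one at Visit 8 is at the investigator's discretion, and the extension has no formal follow-up visit. If 14.6 is applied, Visit 7 describes complete responders only, a subset of those whom 18.1 counts. An analysis plan cannot repair this, because it cannot recover an examination that was never done.

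**Working it through.** The protocol gives no power, assumed response rate or derived sample size for this point (18.2: "The trial is an exploratory, open, pilot trial, so a power calculation is inappropriate"), so there is no figure to reproduce. The check is a cross-reading, followed by an illustration of size.

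**Step 1. Apply each rule to the same patient.** Take 8 carcinoids at baseline. Reduction in number = 1 − (count at Visit 6 ÷ 8). I read the 25% in 18.1 as at least 25%.

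| Finding at Visit 6 | Responder in 18.1? | 2.6, 9, 6.1, 6.2 | 14.6 |
|---|---|---|---|
| 8 to 0 (100%) | yes | Visit 7 | Visit 7 |
| 8 to 1 (87.5%) | yes | Visit 7 | leaves |
| 8 to 2 (75%) | yes | Visit 7 | leaves |
| 8 to 6 (25%) | yes | Visit 7 | leaves |
| 8 to 7 (12.5%), same size | not by number or size | depends on what counts as regression | leaves |
| 8 to 8, same size, ECL density down 25% | yes | no visible regression: no Visit 7 | leaves |

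Rows 2 to 4 are the direct contradiction. The last two rows show that the four consistent statements do not coincide with 18.1 either. Regression has no threshold. The ECL-density route cannot be judged by eye at Visit 6, and the single blinded pathology read takes place only at the end of the study (14.14).

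**Step 2. What is and is not lost.** Section 14.6 schedules gastroscopy, biopsies and bloods at Visit 6 before the patient leaves. Week-12 response under 18.1 is therefore observed whichever rule is used. The loss is Visit 7: gastroscopy, gastrin and CgA.

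**Step 3. Illustration of size.** N = 10 is the protocol maximum. Two rates are assumed, since the protocol gives neither: r, the share of patients who respond (40–80%), and c, the share of responders with complete regression at Visit 6 (10–50%). It is also assumed that all 10 reach Visit 6 and that every responder has visible regression.

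- Reaching Visit 7 if regression suffices: 10 × r = 4 to 8.
- Reaching Visit 7 under 14.6: 10 × r × c = 0.4 (r = 0.4, c = 0.1) to 4 (r = 0.8, c = 0.5).
- Responders without Visit 7 under 14.6: 10 × r × (1 − c) = 2.0 (r = 0.4, c = 0.5) to 7.2 (r = 0.8, c = 0.1).
- Chance that nobody reaches Visit 7 by way of Visit 6 under 14.6: (1 − r × c)^10, from 0.60^10 = 0.6% to 0.96^10 = 66%.

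**Step 4. Extension entry.** Read literally, benefit from 12 weeks' treatment does not fit complete responders at Visit 4, who stopped at 6 weeks. Partial responders at Visit 6 have had 12 weeks, but 14.6 has already taken them out of the trial. Patients first found to be tumour-free at Visit 6 fit both texts. For the other two groups the text does not settle eligibility.

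**The case against.** The strongest reply is that this is one stray line in a small exploratory pilot. Four statements agree, 14.6 is the outlier, and sites may well follow the majority. Off-treatment durability is not among the objectives in Section 8 or the endpoints named in 18.1. Part of this stands: the protocol sets no order of precedence between sections, so the loss is a risk that depends on 14.6 being followed. But 14.6 is the step-by-step list for the visit, and with at most 10 patients each missing Visit 7 counts.

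Four stronger readings are tempting and are not supported:

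- *That the protocol has several rival definitions of response.* It has one, in 18.1. The regression wording routes patients between visits; the fault is that it conflicts with itself and is not linked to 18.1.
- *That the primary response rate changes with the rule.* The routing decides who attends Visit 7, not who meets the 25% criterion at week 12.
- *That the Visit 10 branch, "if on visual inspection gastric carcinoids are still present: continue treatment with YF476 once daily", proves that the extension expects the patients whom 14.6 removed.* A complete responder whose carcinoids return off treatment fits that branch too. Nor do the entry conditions mention attendance at Visit 7, so the extension is not shown to be empty.
- *That Visit 7 attenders must be exactly the 18.1 responders.* That would choose a follow-up rule, and one that could not be applied at Visit 6 to the ECL-density route.

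**Conclusion.** The contradiction is real and lies in current text. A patient with partial regression continues under the summary, Section 9 and both flow charts and is discharged under 14.6, although that patient can be a responder under 18.1 and 14.7 offers Visit 7 to those who respond.

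If 14.6 is followed, the off-treatment data describe complete responders only. Under the assumed rates, that leaves 2.0 to 7.2 of 4 to 8 expected responders without Visit 7. Those counts show scale only; the contradiction itself does not depend on them. Extension entry is unclear for partial responders at Visit 6 and for complete responders at Visit 4. The week-12 response rate is not affected by the routing rule.

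**What to change.** 1. Reconcile 2.6, 6.1 (note 3), 6.2 (note 5), 9, 14.6 and 14.7 so that one Visit 6 rule applies throughout. Which rule is a clinical decision for the sponsor and investigator.
2. State how regression at Visit 6 and responding in 14.7 relate to the response definition in 18.1, noting that the ECL-density component cannot be judged visually at that visit.
3. Reconcile the extension entry wording in 2.6, 9 and 14.7 with the Visit 4 stopping text in 14.4 and with the chosen Visit 6 rule, and say what is meant by having benefitted.
4. If the complete-regression rule is kept, state in the report that Visit 7 results apply to complete responders only.

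The cost is a wording amendment. No visit is added beyond those already in Sections 6 and 9.

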### 14.7 Visit 7: 12 weeks after stopping YF476

Visit 7 will be a follow-up visit for patients who respond to YF476. The gastroscopy and blood sampling for fasting gastrin and CgA will be repeated.

Some patients will be eligible for extended treatment with YF476, as described below. To be eligible for further treatment, the patient must have benefitted from 12 weeks' treatment, and have tolerated YF476 well, and must give fully informed written consent.

### 14.8 Visit 8

The investigator will:

• tell the patient about the extended dosing period and ask him or her to read the information about the extended dosing and sign the consent form;

- do a gastroscopy and take gastric biopsies if the investigator thinks that a new baseline gastroscopy is necessary. If this is the case, the patient will have been told in advance and will be asked to fast for ≥6 h before the visit;
- collect blood for safety tests and for assay of fasting levels of gastrin and CgA if the investigator thinks that new baseline values are necessary;
- give the patient a container of YF476 capsules (25 mg) and instructions on how many to take daily with breakfast, starting the following day; and
- give the patient a diary card, to record YF476 doses, any adverse events, and any concomitant medication.

# 14.9 Visit 9: 12 weeks after starting extended YF476 dosing

The investigator will:

- check that the patient has fasted;
- collect the diary card, and issue a new one;
- check the diary card for compliance with treatment, and for adverse events and concomitant medication;
- collect YF476 container and assess compliance;
- record a 12-lead ECG, and blood pressure and heart rate;
- collect blood and urine for safety tests, including a pregnancy test for women of child-bearing potential;
- collect blood for assay of fasting levels of gastrin, CgA, YF476 (trough), and serum for storage;
- after taking the fasting blood sample, give the patient their dose of YF476, wait 1 h, and then collect blood for assay of peak concentration of YF476;
- issue a new container of YF476 capsules (25 mg) to be taken with breakfast as before; and remind the patient to fast before their gastroscopy on Visit 10.

# 14.10 Visit 10: 24 weeks after starting extended YF476 dosing

The investigator will repeat the procedures from visit 9 and:

- do a gastroscopy and take gastric biopsies, and proceed as follows:
  - if on visual inspection the gastric carcinoids have regressed completely: stop YF476, omit Visits 11 and 12, providing all safety assessments prove satisfactory; or
  - if on visual inspection gastric carcinoids are still present: continue treatment with YF476 once daily.

• after collecting the fasting blood sample and doing the gastroscopy, give the patient their dose of YF476, wait 1 h, and then collect blood for assay of peak YF476 concentration; and instruct the patient about Visit 11.

# 14.11 Visit 11: 36 weeks after starting extended YF476 dosing

The investigator will:

- check that the patient has fasted;
- collect the diary card, and issue a new one;
- check the diary card for compliance with treatment, and for adverse events and concomitant medication;
- collect YF476 container and assess compliance;
- record a 12-lead ECG, and blood pressure and heart rate;
- collect blood and urine for safety tests, including a pregnancy test for women of child-bearing potential;
- collect blood for assay of fasting levels of gastrin, CgA, YF476 (trough), and serum for storage;
- after taking the fasting blood sample, give the patient their dose of YF476, wait 1 h, and then collect blood for assay of peak concentration of YF476;
- issue a new container of YF476 capsules (25 mg) to be taken with breakfast as before; and remind the patient to fast before their gastroscopy on Visit 12.

